2. SYNOPSIS

Study Title	Oxford Haemodynamic Adaptation to Reduce Pulsatility: Randomised, placebo controlled, crossover study of effects of sildenafil on cerebral arterial pulsatility in patients with cryptogenic or lacunar stroke and small vessel disease
Internal ref. no. (or short title)	OxHARP
Study Design	Randomised, placebo-controlled, double-blind, crossover study

Study Participants	Cryptogenic or lacunar stroke or TIA, with mild to moderate small vessel disease changes on MRI or CT	
Planned Sample Size	75	
Treatment duration	3 weeks per treatment (12-14 weeks in total)	
Follow up duration	11 to 15 weeks	
Planned Study Period	36 months	
	Objectives	Outcome Measures
Primary	Assess whether 3 weeks of treatment with sildenafil (a PDE5 inhibitor) reduces cerebral arterial pulsatility on transcranial ultrasound, compared to placebo in patients with chronic vascular injury to the brain (small vessel disease)	Gosling's MCA pulsatility index on Transcranial ultrasound (MCA-PI)
Secondary	1) Assess whether 3 weeks of treatment with sildenafil (a PDE5 inhibitor) alters cerebral arterial reactivity to carbon dioxide on transcranial ultrasound, compared to placebo 2) Assess whether 3 weeks of treatment with sildenafil (a PDE5 inhibitor) has non-inferior effects on cerebral arterial pulsatility and reactivity to carbon dioxide on transcranial ultrasound, compared to cilostazol (a PDE 3 inhibitor)	1) and 2) Change in mean flow velocity on TCD before vs during CO2 challenge
Tertiary Objectives 1) Assess whether 3 weeks of treatment with sildenafil or cilostazol increases cerebral arterial reactivity to carbon dioxide on MRI, compared to placebo 2) Biochemical / genetic predictors of response to treatment	Reactivity of BOLD signal on MRI to CO2 challenge Markers of endothelial function (e.g. ICAM, VEGF, vWF) and genetic targets of the medications in the trial	After 3 weeks of treatment with sildenafil and cilostazol versus placebo Analysed in the 2 years after the last visit of the last participant.

Investigational Medicinal Product(s)	Sildenafil Cilostazol
Formulation, Dose, Route of Administration	Sildenafil: Oral 25 - 50mg tds, tablet Cilostazol: Oral, 50 - 100mg, BD, tablet (with mid-day placebo) Placebo: Oral, TDS

3. ABBREVIATIONS

AE	Adverse event
AR	Adverse reaction
CI	Chief Investigator
CO2	Carbon dioxide
CRA	Clinical Research Associate (Monitor)
CRF	Case Report Form
CRO	Contract Research Organisation
CT	Computed Tomography (brain scan)
CTA	Clinical Trials Authorisation
CTRG	Clinical Trials and Research Governance
DMC/DMSC	Data Monitoring Committee / Data Monitoring and Safety Committee
DSUR	Development Safety Update Report
etCO2	End-tidal carbon dioxide
GCP	Good Clinical Practice
GP	General Practitioner
HRA	Health Research Authority
IB	Investigators Brochure
ICF	Informed Consent Form
ICH	International Conference on Harmonisation
IMP	Investigational Medicinal Product
IRB	Independent Review Board
MCA-PI	Middle cerebral artery pulsatility index
MHRA	Medicines and Healthcare products Regulatory Agency
N2	Nitrogen
NHS	National Health Service
NRES	National Research Ethics Service

PDE5	Phosphodiesterase 5 inhibitor
PI	Principal Investigator
MCA-PI	Middle cerebral artery pulsatility index (Gosling's)
PIL	Participant/ Patient Information Leaflet
R&D	NHS Trust R&D Department
REC	Research Ethics Committee
SAE	Serious Adverse Event
SAR	Serious Adverse Reaction
SDV	Source Data Verification
SMPC	Summary of Medicinal Product Characteristics
SOP	Standard Operating Procedure
SUSAR	Suspected Unexpected Serious Adverse Reactions
TMF	Study Master File
TSG	Oxford University Hospitals NHS Foundation Trust / University of Oxford Trials Safety Group

4. BACKGROUND AND RATIONALE

Chronic injury to the small vessels of the brain ('small vessel disease') is associated with acute stroke,¹ progressive cognitive decline,² late-onset refractory depression,³ functional impairment in daily living⁴ and increased mortality.⁵ Originally defined on pathological grounds, it is now recognised primarily on brain imaging by a pattern of white matter hyperintensities on T2-based imaging in the periventricular and deep white matter, or acute lacunar strokes, cerebral microbleeds and dilated perivascular spaces.⁶ Despite accounting for more than 30% of strokes and 40% of dementia,⁷ the underlying mechanism of small vessel injury is unclear and may reflect systemic haemodynamic influences on the cerebral vasculature, such as increased transmission of pulsatile blood pressure to the brain⁸ or inherent dysfunction of the small vessels and their endothelium.⁹ However, white matter hyperintensities are highly prevalent in the population, affecting the majority of patients over the age of 65 and many patients with advanced imaging changes of SVD remain functionally independent.¹⁰ As such, it is important to target novel treatments at those patients with SVD who are at an increased risk of morbidity.

The underlying cause of many strokes remains undefined despite intensive investigation ('cryptogenic' stroke), indicative of a major gap in our understanding of the pathophysiology of stroke and resulting in significant excess morbidity.¹¹ In patients with small vessel disease, acute stroke due to small vessel occlusion (lacunar stroke) is commonly recognised as the principle type of stroke, but cryptogenic stroke remains common. Furthermore, classification of lacunar stroke relies upon clinical and imaging criteria rather than demonstration of an *in situ* occlusion of a perforating small vessel. This can therefore result from multiple aetiologies and rates of misclassification of lacunar events are high. Given this aetiological uncertainty, the diffuse cerebral arteriopathy of small vessel disease is likely to contribute to both lacunar stroke and cryptogenic strokes.¹² Lacunar and cryptogenic strokes are therefore a marker of an increased risk of morbidity in the context of chronic SVDs, and identification of an effective treatment for the associated arteriopathy may also offer a novel intervention for a large number of cryptogenic strokes that currently have no specific treatment option.¹²

Hypertension is the strongest modifiable risk factor for small vessel disease, but there is only limited evidence that reduction of blood pressure alone significantly reduces progression of development of SVD.¹³ However, pulsatility of blood flow in the brain is associated with small vessel disease,⁸ resulting from increased transmission of the pulsatile aortic waveform to the brain through stiff conduit vessels. Secondly, there is significant endothelial dysfunction in SVDs, with increased breakdown of the blood-brain barrier detected by increased extravasation of contrast material on MRI in both white matter hyperintensities and normal appearing white matter.¹⁴ This

may be secondary to factors such as hypertension or arterial pulsatility, or it may reflect an underlying, primary endotheliopathy.

Aortic pulsatility, aortic stiffness and transmission of the aortic waveform are increased by reflection of the outgoing aortic pressure wave from the distal small vessels back towards the aorta, increasing aortic pulsatility. The resulting enhanced pulsatility of blood reaching the low resistance small vessels in the brain causes increased shear stress during systole and potential hypoperfusion of tissues during diastole.¹⁵ This is potentially modifiable by vasodilating medications that delay the site and severity of wave reflection, reducing aortic pulsatility. Such medications may also act upon muscular conduit vessels (distal ICA / MCA) to increase elasticity, improve dampening of the aortic waveform and reducing pulsatility at distal vessels.

Endothelial dysfunction is associated with abnormalities of vasodilation and vasoconstriction, controlled through the endothelial nitric oxide – cGMP pathway.¹⁶ This can be tested by measuring the cerebral blood flow response to carbon dioxide,¹⁷ with either transcranial ultrasound or MRI imaging. A number of agents have the potential to effect the endothelium. Phosphodiesterase inhibitors reduce breakdown of cGMP, potentiating the nitric oxide driven vasodilation of small arterioles. Phosphodiesterase 5 inhibitors (sildenafil, tadalafil) have been widely used in erectile dysfunction and in another occlusive vasculopathy (pulmonary arterial hypertension), with an established safety profile and tolerability. A number of studies have demonstrated a potential benefit of sildenafil on endothelial function,¹⁸ but this has not been assessed specifically in cerebral small vessel disease. Cilostazol is a phosphodiesterase 3 inhibitor that has been tested in clinical trials of patients with stroke with a reduction in recurrent events during follow up,¹⁹ potentially explained by a reduction in cerebral arterial pulsatility.²⁰ Polymorphisms in the PDE3 gene have also been shown to be associated with stroke risk in genome-wide association studies.²¹ However, it has an additional antiplatelet effect, complicating understanding of how its pharmacological effects translates into clinical outcomes, and complicating its use in clinical practice.

This study therefore aims to test the physiological effect of sildenafil, a phosphodiesterase 5 inhibitor, on cerebral arterial pulsatility, with secondary assessment of effects on cerebrovascular endothelial function. This will be tested at doses consistent with those tolerated in pulmonary arterial hypertension. It will be tested in recovered patients with a previous cryptogenic or lacunar stroke or probable TIA requiring treatment, and mild-moderate small vessel disease. This will allow assessment of effects on cerebrovascular physiology in the presence of small vessel injury, but prior to establishment of likely irreversible changes. Secondly, patients will then receive cilostazol, to compare the relative effect of PDE5 inhibition and PDE3 inhibition on cerebrovascular haemodynamics as a secondary outcome measure.

5. OBJECTIVES AND OUTCOME MEASURES

[figure not shown]
Objectives	Outcome Measures	Timepoint(s)
Primary Objective Assess whether 3 weeks of treatment with sildenafil (a PDE5 inhibitor) reduces cerebral arterial pulsatility on transcranial ultrasound, compared to placebo in patients with chronic vascular injury to the brain (small vessel disease)	Middle cerebral arterial pulsatility index ((Gosling's PI = peak systolic velocity – end diastolic velocity)/(mean flow velocity)) on transcranial ultrasound	Baseline, after 3 weeks of treatment with placebo versus 3 weeks of sildenafil
Secondary Objectives 1) Assess whether 3 weeks of treatment with sildenafil (a PDE5 inhibitor) alters cerebral arterial reactivity to carbon dioxide on transcranial ultrasound, compared to placebo 2) Assess whether 3 weeks of treatment with sildenafil (a PDE5 inhibitor) has non-inferior effects on cerebral arterial pulsatility and reactivity to carbon dioxide on transcranial ultrasound, compared to cilostazol (a PDE 3 inhibitor)	Percentage increase in MCA velocity on 6% CO ₂ vs medical air As above	As above
Tertiary Objectives 1) Assess whether 3 weeks of treatment with sildenafil (a PDE5 inhibitor) or cilostazol increases cerebral arterial reactivity to carbon dioxide on MRI, compared to placebo 2) Determine biochemical / genetic predictors of response to treatment	Reactivity of BOLD signal on MRI to CO ₂ challenge Markers of endothelial function (e.g. ICAM, VEGF, vWF) and genetic targets of the medications in the trial	After 3 weeks of treatment with sildenafil or cilostazol versus placebo Analysed in the 2 years after the last visit of the last participant.

6. STUDY DESIGN

This is an investigator-led, randomised, placebo and actively controlled, double-blind (patient and clinician), assessor-blinded, crossover design study. 75 participants will be consented and assessed at a baseline visit, undergo a clinical assessment, followed by a research assessment including transcranial ultrasound to determine cerebral arterial pulsatility and reactivity. They receive three treatments in

randomised sequence: placebo (one tablet TDS, titrated to 2 tablets after 1 week), cilostazol (50mg bd, titrated to 100mg bd, with midday placebo) or sildenafil (25mg tds, titrated to 50mg tds)- NB titration up only happens if the participant is not on omeprazole. After each treatment, the will undergo a repeat clinical and physiological assessment, followed by at least 1 week washout before starting the next treatment. However, the washout may be prolonged if unavoidable (ie due to the COVID-19 pandemic). A subgroup of 60 participants will undergo MRI imaging when on sildenafil and placebo to assess arterial pulsatility on MRI and cerebrovascular reactivity, whilst 30 will undergo MRI on all three treatments.

FLOWCHART

Sequence	Drug 1	Drug 2	Drug 3
1	Sildenafil	Placebo	Cilostazol

2	Sildenafil	Cilostazol	Placebo
3	Cilostazol	Sildenafil	Placebo
4	Cilostazol	Placebo	Sildenafil
5	Placebo	Sildenafil	Cilostazol
6	Placebo	Cilostazol	Sildenafil

[figure not shown]
Screening phone-call ,patient invited and PIS sent in advance

Screening Visit:
Review eligibility
Detailed explanation of trial

CONSENT

Medical History & Examination
Blood tests / Pregnancy Test / ECG
Review medical records (if necessary)

Drug Allocation

7. PARTICIPANT IDENTIFICATION

7.1. Study Participants

75 patients with a history of a cryptogenic or lacunar stroke or probable TIA requiring treatment more than 1 month previously and mild-moderate small vessel disease.

7.2. Inclusion Criteria

- Participant is willing and able to give informed consent for participation in the study.
- Male or Female, aged 18 years or above.
- Can record MCA waveform on at least one side ('useable TCD window')
- Non-disabling, ischaemic stroke or probable TIA requiring treatment, >1 month prior to randomisation, of either cryptogenic or lacunar aetiology, confirmed clinically or on brain imaging
- White matter hyperintensities on MRI (Fazekas scale) or CT (Blennow scale) consistent with cerebral small vessel disease:
 - Age <60: MRI - Fazekas score 1 – 3 (max 2 points in periventricular or deep score)
 CT – Blennow score 1 – 3 (max 2 points in periventricular or deep score)
 - Age >60: MRI - Fazekas score 1 – 4 (max 2 points in periventricular or deep score)
 CT – Blennow score 1 – 4 (max 2 points in periventricular or deep score)

7.3. Exclusion Criteria

- Pregnant or breastfeeding women, women of childbearing age not taking contraception.
 - Acceptable contraception in women of childbearing age is a "highly effective" contraceptive measure as defined by the Clinical Trials Facilitation Group (http://www.hma.eu/fileadmin/dateien/Human_Medicines/01-About_HMA/Working_Groups/CTFG/2014_09_HMA_CTFG_Contraception.pdf) and includes combined (oestrogen and progesterone containing) or progesterone-only contraception associated with inhibition of ovulation, or intrauterine device or bilateral tubal occlusion
- Other major neurological or psychiatric conditions affecting the brain and interfering with the study design (e.g. multiple sclerosis)
- Other causes of stroke such as
 - ≥50% luminal stenosis (NASCET) in large arteries supplying the infarct area

- major-risk cardioembolic source of embolism (permanent or paroxysmal atrial fibrillation, sustained atrial flutter, intracardiac thrombus, prosthetic cardiac valve, atrial myxoma or other cardiac tumours, mitral stenosis, recent (<4 weeks) myocardial infarction, left ventricular ejection fraction less than 30%, valvular vegetations, or infective endocarditis)
 - other specific causes of stroke (e.g. arteritis, dissection, drug misuse)
- Large vessel occlusion on MRA or CTA (carotid, basilar or MCA)
- Modified Rankin Score >3 (requires assistance to walk)
- Unable to swallow
- Renal impairment (eGFR <35ml/min)
- Significant biochemical abnormalities (sodium <130, K+ <2.5 or >5.5, LFTs >3 x upper limit of normal range)
- Life expectancy <2 years
- Contraindication to active agents
 - Concurrent use of alphablocker
 - Regular use of nitrate (ISMN, GTN, other)
 - Heart failure (NYHA 2-4)
 - Severe aortic stenosis
 - Bilateral renal artery stenosis
 - Uncontrolled arrhythmias
 - Previous priapism
 - Anatomical deformation of the penis
 - Recent myocardial infarction (within 6 months)
 - Unstable angina
 - History of non-arteritic ischaemic optic neuropathy
 - Hypotension: BP <90/60
 - Haemodynamically significant aortic / mitral valve disease
 - Sickle cell disease, myeloma, leukaemia
 - Uncontrolled hypertension (BP >180/110 despite treatment with 3 antihypertensives)
- Scheduled elective surgery or other procedures requiring general anaesthesia during the study.
- Any other significant disease or disorder which, in the opinion of the Investigator, may either put the participants at risk because of participation in the study or the participant's ability to participate in the study.

- Participants who have participated in another research study involving an investigational product in the past 12 weeks.
- Use of an anticoagulant (warfarin, dabigatran, rivaroxaban etc) or more than one antiplatelet drug.
- Predisposition to intracerebral haemorrhage (previous ICH, likely cerebral amyloid angiopathy) or intraocular haemorrhage (uncontrolled diabetic retinopathy or neovascularisation)
- Allergy to constituents of medications or components of placebo / overencapsulation
- Use of CYP induces that interact with study medications (ketoconazole, erythromycin).

Exclusion criteria specific for MRI substudy:

- Not able to transfer to MRI scanner
- Active respiratory illness (such as moderate to severe asthma or COPD) such that they are unable to tolerate MRI or unable to lie flat
- Claustrophobia
- Contraindication to MRI scan (pacemaker, aneurysm clip etc)
- Other significant brain disorder that may confound interpretation of MRI imaging (multiple sclerosis, brain tumour)

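### The entry criterion bars only regular nitrate use, so a patient who holds as-needed GTN could be randomised although every sequence includes sildenafil

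*Protocol*

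**What the plan says.** Protocol 7.3 has an exclusion headed "Contraindication to active agents" with a list beneath it. The nitrate entry in that list reads "Regular use of nitrate (ISMN, GTN, other"). The entry directly above it, "Concurrent use of alphablocker", has no frequency limit. Neither does the separate exclusion "Use of an anticoagulant (warfarin, dabigatran, rivaroxaban etc) or more than one antiplatelet drug".

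Protocol 9.5 governs medication during the study. It prohibits concomitant nitrates (naming GTN, ISMN and nicorandil) with no reference to regularity. It also prohibits alpha-blockers, other PDE5 and PDE inhibitors, direct vasodilators, anticoagulants and more than one antiplatelet agent. A participant who comes to need one of these is to be withdrawn.

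Protocol section 8 assigns a study number and treatment schedule once the eligibility criteria are met; it does not refer to 9.5 at that step. The sequence table in Protocol section 6 contains sildenafil in all six rows, at 25 mg three times daily rising to 50 mg. The SAP adds nothing on nitrates.

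**The concern.** The protocol itself treats nitrates as a contraindication to the study drugs, yet the rule that decides entry is narrower than the rule that applies after entry. The word 'regular' leaves out as-needed use, which is a common way of holding GTN. A patient with stable angina and a GTN spray is an example: stable angina is not a named exclusion, since the ischaemic cardiac entries are "Unstable angina" and "Recent myocardial infarction (within 6 months").

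Such a patient may need a nitrate without warning. Treatment is blinded, and Protocol 8.4 provides no out-of-hours code-break, on the ground that no complication would call for an intervention that depends on knowing the current treatment. For someone who may take a nitrate, the current treatment does matter. That leaves the entry criterion as the main protection.

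**Working it through.** The plan gives no figure to reproduce. The check compares the two rules and then sizes the overlap under a stated assumption.

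**1. Classes barred in 9.5 against 7.3**

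| Class barred in Protocol 9.5 | Protocol 7.3 |
|---|---|
| Alpha-blockers | Matched |
| Anticoagulants | Matched |
| More than one antiplatelet | Matched |
| Nitrates | In part: regular use only |
| PDE5 inhibitors | Not named |
| Other PDE inhibitors (cilostazol) | Not named |
| Direct vasodilators | Not named |

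That is 3 matched + 1 in part + 3 not named = 7. Only the nitrate line is put forward as a safety gap; the three unnamed classes show that 7.3 was not aligned with 9.5.

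**2. Who gets through**

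- *Regular nitrate user:* excluded by 7.3.
- *Known current as-needed user:* not caught by the wording of 7.3, but should be stopped by 9.5, because the visit schedule in Protocol section 8 records concomitant medication at screening and baseline.
- *Carrier who is not using the nitrate at entry:* not a regular user under 7.3, and not in concomitant use under 9.5. The withdrawal rule acts when a need arises, which for as-needed GTN can be the moment of the dose. Use between visits may come to light only at the next medication review.

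**3. Chance of overlap for one dose**

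Assumption: a carrier enters and takes one nitrate dose on a day drawn uniformly between first study dose and last visit. The chance that it falls in the sildenafil phase is

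sildenafil days / total days, with 3 weeks = 21 days on sildenafil.

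| Last visit | Source | Total days | Chance |
|---|---|---|---|
| 11 weeks | Protocol 8.6; also 3 × 21 + 2 × 7 | 77 | 21/77 = 27% |
| Day 84 | Visit schedule, Protocol section 8 | 84 | 21/84 = 25% |
| 13 weeks | Protocol 8.6 | 91 | 21/91 = 23% |

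Prolonged washouts lower these values. The section 8 rule that lets an interrupted three-week course be started again would raise them if the repeated course is sildenafil.

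**The case against.** Several safeguards stand in the way.

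- **The parent exclusion.** "Contraindication to active agents" is an exclusion in its own right, and naming GTN shows an intention to ask about it. This reading is open. But the heading does not mark its list as examples, unlike "Other causes of stroke such as" in the same section, and a screener who finds a specific nitrate line may take it as the whole rule. The contrast in wording is only modest evidence.
- **The 9.5 trigger is clinical need, not the taking of a dose.** A current as-needed prescription could be read as an existing need, visible on the medication list before dispensing. If so, 9.5 bars a patient whom 7.3 admits, and the two rules conflict. If not, both miss the carrier. Either way the entry wording needs changing.
- **Medical review before dosing.** There is a full history, examination, record review and consent by a study physician, plus a discretionary exclusion: "Any other significant disease or disorder which, in the opinion of the Investigator, may either put the participants at risk". These make entry unlikely, but the last is a judgement about disease, not a rule about medication.
- **A prescription clause is stricter than 9.5.** True, and deliberate: merely deleting 'regular' would still leave a rule about use.
- **The percentages are conditional.** Also true. They are phase length over study length and say nothing about how many carriers would enter.

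It also stands that no entry criterion can prevent a need that first appears during the study, and that the participant information sheet, which is not among the documents, may carry a warning.

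**Conclusion.** The concern holds on a literal reading. As worded, the entry rule admits a patient who holds an as-needed nitrate into a trial where completing any sequence means a sildenafil phase, despite a contraindication that the protocol recognises. The safeguards make harm unlikely without closing the gap. The change should be made on safety grounds; confidence is medium because a careful screener could reach the right answer from the parent heading or from 9.5.

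The 23% to 27% overlap rests on the one-dose, random-day assumption and on an uninterrupted 21-day sildenafil phase. The number of carriers is unknown, and none is estimated. Nothing here touches the primary analysis or the sample size.

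**What to change.** 1. In Protocol 7.3, replace the nitrate line with: *Any use of a nitrate or nicorandil, regular or as-needed, including a current as-needed GTN prescription.*
2. Add to 7.3: *Use of any medication prohibited in section 9.5.*
3. Check both against the medication list at screening and again before randomisation.
4. If recruitment has closed, use the lists already collected to see whether anyone with an as-needed nitrate was enrolled.

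The cost is protocol wording and one line on the screening form. Some candidates who hold an as-needed nitrate would be screened out; the documents do not allow that number to be given.
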